3.5. Withdrawal Criteria

Subject will be withdrawn from the study if the subject is unable to tolerate the SURE program

3.6. Subject Replacement

Subjects who drop out will be replaced

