3. STUDY POPULATION

3.1. List the number of subjects to be enrolled.

20 subjects will be randomly assigned to a control (N=10) and experimental group (N=10). 4 normal healthy subjects will also be recruited for fMRI investigations.

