6.1. Randomisation and Blinding

Random assignment of subjects will be done using the randomizer found in the web (www.Randomizer.org/form.htm). A non-team member will generate the randomized allocation sequence, seal the group numbers in individual envelopes, and arrange them according to the randomized allocated sequence. These envelopes will be kept under lock and key in TTSRHC. The same non-team member will pass these sealed envelopes in accordance to the randomized allocated sequence one at a time to the CPI who will enrol and assign the eligible subjects to their groups. The unmasking of the randomization will be at the end of data collection and fMRI analysis. A blinded assessor will perform all the clinical assessments. The I2R who will be performing the fMRI analysis will be blinded to the group which the subjects are in.

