11. SAMPLE SIZE AND STATISTICAL METHODS

11.1. Determination of Sample Size

Since this study is a pilot exploratory trial, results of individual subjects from each group will be analysed in

detail to determine the difference in brain neuroplasticity between the control and experimental groups. N=10 from each group is chosen because it is deemed feasible to recruit stroke patients who will be willing to participate in this study clinically in the period of 2 years (the time period of the funding).

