11.2. Statistical and Analytical Plans

a. Study Statistical Analysis

Statistical analysis will be performed using STATA version 10.0 for Windows (StataCorp, TX, USA). Descriptive statistics will be used to describe subjects' demographics in each group.

Analysis of UL Functional Outcome

Wilcoxon signed-ranked tests will be used at each time points (pre, 2 weeks after start of intervention, post, 1month post-intervention, 3months post-intervention) to compare UL functional outcomes between the experimental and control groups. The significance level for all statistical tests will be set at $p<0.05$ levels. All data will be analysed by intention to treat.

Analysis of feasibility of accelerometers to measure affected UL use

Analysis of the compliance rate and responses from the questionnaire will be used to determine the feasibility and acceptance of using accelerometers to measure affected UL use after stroke.

Analysis of SURE Program's feasibility

Wilcoxon signed-rank test will also be used to compare outcomes of pain, fatigue and spasticity pre-and post-intervention period. The differences in the duration of affected UL use per day and the ratio of affected UL use/ non-affected UL use between the experimental group and control group (from the accelerometer recordings), the rate of compliance, the proportion of subjects who successfully complete the whole training, and the dropout rate will be calculated to assess the feasibility of **SURE Program**.

Analysis of fMRI investigation

Comparison of activation in primary motor cortex, secondary motor cortex and cerebellar hemisphere for bilateral sides will be done by comparing mean percentage signal change (%SC), absolute voxel counts (VC) and changes in geometric centers of these areas on both sides¹⁷. In addition, a laterality index (LI) will also be calculated to determine the relative cortical activity. Asymmetry has been found to restore to normal (L=1.0) when the affected hand movement improved after rehabilitation⁴¹.

Analysis of resting state fMRI/DTI

Functional connectivity and tract integrity^{32,38} will be studied by FSL with the normalization method^{39,40}. The secondary degeneration of the brain in the remote region to the primary lesion will also be studied for the sub-groups of subjects with less motor recovery³⁰.

MRS analysis

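### Section 3.6 replaces every drop-out, even after randomisation, without saying which group the replacement joins or how the replaced subject is counted; this puts concealment, intention to treat and the feasibility rates at risk

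*Protocol*

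**What the plan says.** Section 3.6 is one sentence: "Subjects who drop out will be replaced". It has no limit to drop-outs before randomisation. It does not say whether the replacement takes the vacated group or the next allocation, or what happens to the data of the subject who left.

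The sections it has to work with are these:

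- Sections 3.1 and 5 fix 20 patients, 10 per group. Section 11.1 bases this on recruitment alone: "N=10 from each group is chosen because it is deemed feasible to recruit stroke patients".
- Section 6.1 describes one randomised sequence in sealed envelopes: "The same non-team member will pass these sealed envelopes in accordance to the randomized allocated sequence one at a time to the CPI". The CPI is the person "who will enrol and assign the eligible subjects to their groups".
- Section 8.5 makes the CPI one of two people who know the groups. Sections 3.2, 6.3a and 12.1 have the same CPI screen admissions and take consent.
- Section 3.5: "Subject will be withdrawn from the study if the subject is unable to tolerate the SURE program".
- Section 6.3e continues assessments until a subject withdraws from participation. It then says that a subject who leaves the SURE programme will not be pursued for follow-up unless the subject asks, and that all withdrawals and their reasons will be evaluated.
- Section 11.2: "All data will be analysed by intention to treat". The same section uses the dropout rate and the proportion completing training to judge feasibility.

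**The concern.** Replacement before randomisation is harmless. Replacement after randomisation raises two questions that section 3.6 leaves open.

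The first is allocation. Holding 10:10 means putting the new subject into the group that lost one. The CPI knows which group that is and also decides whom to approach next, so the allocation would be known before the subject is chosen. The envelopes exist to prevent exactly that.

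The second is counting. If the replacement stands in for the person who left, the analysed 10 against 10 is not the randomised set, and the dropout and completion rates lose the people they are meant to count.

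The exposure is one-sided. The withdrawal criterion in 3.5 can be met only in the SURE group, and 6.3e makes no effort to follow those who leave the programme. Control subjects have no matching route out.

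**Working it through.** **The plan's own figure.** 10 + 10 = 20 agrees. No power, effect size, standard deviation or drop-out rate is given, so no formula can reproduce the sample size, and replacement protects no stated power.

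**How likely is the rule to be used?** The protocol gives no drop-out rate, so the rates here are assumptions. P(at least one drop-out among 20) = 1 − (1 − d_SURE)^10 × (1 − d_control)^10.

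- 10% and 10%: 1 − 0.9^20 = 0.88.
- SURE 20%, control 10%: 1 − 0.8^10 × 0.9^10 = 0.96.

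**Can the next envelope restore 10:10?** Suppose k subjects leave one group and each replacement takes an independent 1:1 envelope. All k fall in the depleted group with probability 0.5^k: 50% for k = 1, 25% for k = 2, 12.5% for k = 3. Holding 10:10 would therefore usually require assignment to a known group.

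**How long a sequence would be needed?** If 10 completers per arm are meant, the expected number randomised is 10/(1 − d) per arm.

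| Assumed drop-out, SURE / control | Expected number randomised |
|---|---|
| 10% / 10% | 11.1 + 11.1 = 22.2 |
| 20% / 10% | 12.5 + 11.1 = 23.6 |
| 30% / 10% | 14.3 + 11.1 = 25.4 |

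Section 6.1 describes no sequence extended beyond the planned 20.

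**What happens to the feasibility rates?** Let k subjects leave one arm, each be replaced in that arm, and ten complete.

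| k | Dropout, all randomised | Completion, all randomised | Dropout, final ten only |
|---|---|---|---|
| 1 | 1/11 = 9% | 10/11 = 91% | 0/10 |
| 2 | 2/12 = 17% | 10/12 = 83% | 0/10 |
| 3 | 3/13 = 23% | 10/13 = 77% | 0/10 |

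**Reading the sections together.** There are three ways to apply 3.6:

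1. The replacement takes the vacated group. 10:10 is held, but the allocation is known in advance, against 6.1.
2. The replacement takes the next envelope and the drop-out leaves the analysis. Concealment survives, but the set is not the one promised in 11.2.
3. The replacement takes the next envelope and the drop-out stays in the analysis. Concealment and intention to treat both survive, and the groups may be unequal.

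The protocol does not choose among them.

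**The case against.** A reader might infer that 3.6 contradicts the intention-to-treat statement. The text does not support that. Section 3.6 never says that replaced subjects leave the analysis, and 11.2 says all data are analysed by intention to treat. The third reading above satisfies both.

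A reader might also infer that concealment is necessarily broken. Section 6.1 gives sealed envelopes in sequence as the only allocation route, and 3.6 does not override it. Nor does 3.6 say that its purpose is exactly 10 completers per group.

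A third tempting inference is that replacement itself inflates the SURE result by filling the arm with those who stay. A model with drop-out in SURE only and no true effect does not bear this out. With two drop-outs perfectly correlated with recovery, the mean of the remaining completers rises by 0.274 SD if they are replaced to ten (the two lowest of 12 removed), but by 0.317 SD if they are not replaced (the two lowest of 10 removed). That selection comes from missing outcomes after drop-out, under 3.5 and 6.3e, and not from replacement.

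Finally, this is an exploratory pilot, 6.3e commits to evaluating every withdrawal, and an analysis plan that is not shown may define the analysis set.

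All of this stands, and it limits the point to a risk that the text leaves open. It does not remove the point. Section 3.6 is an enrolment rule that operates during recruitment, and an analysis plan cannot restore concealment once it has been lost. The harmless reading is nowhere stated, and the word used is replacement, not addition. Evaluating withdrawals does not settle the denominator.

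**Conclusion.** The point holds as a gap that endangers three things: the concealment of 6.1, the intention-to-treat set of 11.2 and the feasibility denominators. It should be fixed, ideally before the first subject is enrolled.

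The rule would probably be used: the chance is 88% to 96% under assumed drop-out of 10% in control and 10% to 20% in SURE. If vacated groups are filled, the CPI knows every replacement's allocation in advance. The reported dropout for three losses in one arm could be 23% or zero. The drop-out rates are assumptions, since the document gives none. The denominators are plain arithmetic. No size of bias in the ULFM or ARAT comparison is claimed for replacement.

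**What to change.** Reword section 3.6 so that:

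- only subjects who leave before their envelope is opened are replaced;
- any further subject takes the next unopened envelope of a concealed sequence extended in advance, and is never assigned to a vacated group;
- every subject whose envelope has been opened stays in the assigned group for the intention-to-treat analysis and counts in the dropout and completion denominators.

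Add the extended sequence to section 6.1. Reconcile 3.5 and 6.3e with 11.2, so that outcome assessments continue after a subject stops the programme, where the subject consents. This concerns data collection only, not who should stop the programme. Without it, drop-outs may be in the analysis set by name but have no outcome values.

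The cost is one paragraph in 3.6, a line in 6.1, some extra envelopes, and assessment visits for those who stop but agree to be seen. The arms may end slightly unequal or with fewer than 10 completers. That is acceptable because section 11.1 rests the number on feasibility and makes no power claim.

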4. TRIAL SCHEDULE

	Clinical Assessments (TTSHRC)/ no. of visit	TMS Screening (NUH)/ no. of visit	fMRI Investigations (CIRC@NUS)/no. of visit
Pre-Intervention	1 (Inpatient)	1 (Inpatient)	1 (Inpatient)
Two weeks after start of Intervention	1 (Inpatient)	NIL	NIL
Post-Intervention	1 (In/ Outpatient)	NIL	1 (In/ Outpatient)
One Month Post-Intervention	1 (Outpatient)	NIL	NIL
Three Months Post-Intervention	1 (Outpatient)	NIL	1 (Outpatient)

SURE program intervention will start after pre-intervention TMS screening, clinical assessment and fMRI investigations. It consists of 4 weeks of additional 1 hour daily self-exercise and functional use of affected UL in the hospital ward 6 days a week. The subjects will require to wear an accelerometer on unaffected wrist for 3 weekdays of first week to establish baseline of use, and wear an accelerometer on affected wrist 3 weekdays (8am -8pm each day) per week so that the actual affected UL use can be feedback to subjects during review. Please see attached file: Patient's_Involvement_In_Study_15_April_2017 for summary of each subject's involvement in the study.

5. STUDY DESIGN

Experimental procedure

The subjects will be randomly assigned to a control (N=10) and experimental group (N=10).

Experimental Group

The experimental group will receive one **SURE** program booklet with specific instructions and pictorial illustrations of each exercise and functional use according to their affected ULFM score. There are 3 booklets available (Level 1A for patients with affected ULFM score from 0 to 10; Level 1B for patients with affected

ULFM score from 11 to 22; Level 2 for patients with affected ULM score from 23 to 50). Each **SURE** program booklet consists of stretching exercises, strengthening exercises and performance of simple motor tasks such as reaching, picking up cubes etc. Each exercise will be graded and progressed according to the subjects' affected UL capability by the Clinical Principal Investigator (CPI) who is an experienced principal physiotherapist. The **SURE** program booklet also consists of selected motor tasks to be performed by the subjects using their affected UL. Functional activities such as subjects will be using their affected UL to wipe their faces; wiping the table after eating; applying lotion by the affected hand along the unaffected arm and legs after shower; drinking water from cup/ bottle; lifting and placing affected hand on table top; etc. Each functional motor task will be selected, graded and progressed by the PI according to the subjects' affected UL motor capability during the reviews. The subjects will be taught how to perform the exercises and functional tasks during the first session. The performance of the exercises and functional motor tasks will be reviewed by the CPI three times per week for the first 2 weeks, two times for the third week and one time for the fourth week of intervention period.

The subjects will be asked to perform the exercises 60 minutes (3x 10- 20 minutes) distributed across morning, afternoon, and evening per day for 6 days per week during the 4-week intervention period. They will also be asked to perform the functional tasks as and when is required for their daily function for 6 days per week during the 4-week intervention period. The subjects will be given an Exercise Log to tick and track number of repetitions of the exercises and functional activities each day, the number of days the protocol is completed, and the level of fatigue and pain experienced. If the subject is discharged from the hospital before the 4 weeks of intervention period, he/ she has to carry on with the protocol till the intervention period ends. The CPI will continue to review exercises and the amount of affected UL use with the subjects at home if the subjects are discharged till the intervention period ends.

Control Group

The control group will receive an education booklet with 10 modules. The education booklet will contain information on stroke, recovery and management strategies after stroke. Subjects are to complete 2-3 modules per week and answer 1-2 simple questions after each module. Each module including answering questions takes approximately 5-10 minutes to complete. The CPI will review the information with the subjects 3 times per week for the first 2 weeks, two times for the third week and one time for the fourth week of intervention period.

Both groups will continue with their daily routine therapy sessions in the hospital. The treating therapists will record the duration of therapy of each subject per day.

UL functional outcome measures- ULM and ARAT will be assessed pre-intervention, 2 weeks after start of intervention, post-intervention, 1month and 3months post-intervention. Measures of **SURE** program's feasibility such as VAS pain score, fatigue level, and MAS of biceps and finger flexors will be measured pre-intervention, 2 weeks after start of intervention and post-intervention. A team member who is blinded to which group the subjects are in will perform the outcome measure assessments.

Multimodal imaging for the normal healthy control will be performed once to establish the activation pattern in normal. Multimodal imaging assessment for the patient subjects will be done pre-intervention, post-intervention, and 3months post-intervention.

5.1. Summary of Study Design

The subjects will be randomly assigned to a control (N=10) and experimental group (N=10). The control group will undergo an education program while the experimental group will undergo the **SURE** program. Clinical assessments for both groups will be performed by a blinded assessor at pre, two weeks after start of intervention, immediate post intervention, 1 and 3months post-intervention to determine if the **SURE** program improve affected UL functional outcomes compared with the control group. fMRI investigations will be performed at pre-intervention, post- intervention and 3months post-intervention to determine if the increased UL activity in the **SURE** program influences brain neuroplasticity positively early post-stroke.

6. METHODS AND ASSESSMENTS

Outcome Measures

UL functional outcome measures

UL Fugl Meyer Scale (ULFM)

UL Fugl Meyer Scale will be used to stratify subjects to their level of UL severity and assessment of UL impairment. ULFM score can be subdivided into 3 categories to define the different level of severity of paresis (severe= 0 to 22; moderate=23 to 50; mild>= 51). ULFM will be one of the primary outcome measures to determine UL recovery.

Action Research Arm Test (ARAT)

ARAT will be used as the primary outcome measure of UL functional outcome. ARAT will be one of the primary outcome measures to determine UL recovery.

Measure of UL practice and use

Rating of Everyday Arm-use in the Community and Home (REACH Scale)

The REACH scale is a self-report measure that captures how much an individual with stroke use affected UL outside clinical setting. It has one scale for subjects whose dominant UL is affected and another scale for subjects whose non-dominant UL is affected. It will be used to rate patients' affected UL use after discharge.

Measure of UL practice and use using accelerometry

One tri-axial accelerometer (ActiGraph GT3X+, ActiGraph LLC, Pensacola, Florida) will be placed on subject's unaffected wrist to establish the duration of unaffected UL use in the ward for 3 days in the first week. Another tri-axial accelerometer will be placed on subject's affected wrist for 3 weekdays each week of the 4-week intervention period to assess the amount of affected UL use. The accelerometers will be worn by all subjects (both experimental and control groups) from 8am to 8 pm on the day of donning.

Measures of feasibility of accelerometry in measuring affected UL use

The compliance rate of wearing the accelerometers during the 4 weeks of intervention period will be used to assess compliance. Subjects will also be asked to fill a questionnaire to rate the acceptance, ease, comfort, discomfort, benefits, and problems of wearing the accelerometers in the ward.

*Measures of **SURE** program's feasibility*

The key measure of **SURE** program's feasibility will be the additional affected UL practice and use per day as measured by the accelerometers.

Subjects' fatigue levels will be assessed using 0-10 point Stanford Fatigue Visual Numeric Scale (Stanford Patient Education Research Centre, n.d). Subjects' level of affected UL pain will be assessed using 0-10 rating Visual Analogue Scale (VAS). Subjects' UL spasticity level for biceps and finger flexors will be assessed using Modified Ashworth Scale (MAS). These assessments will be performed pre, 2 weeks in training, and post-training.

SURE program feasibility is also assessed by the compliance rate, dropout rate and any adverse events reported during the intervention period.

Subjects and their caregiver will be asked to fill up a questionnaire to rate on **SURE** program's ease, benefit and overall satisfaction based on VAS (rating 0 -10). In addition, 10 nurses in the ward who have taken care of the stroke patients undergoing the **SURE** program in the ward will also be asked to fill up a questionnaire to rate the ease, difficulty, advantages and disadvantages on **SURE** program implementation in the ward.

TMS Screening

A research staff will apply TMS to the subject. The subject will be seated comfortably and instructed to remain as still as he/ she can. A tight swim cap will be worn by the subject. The vertex will be marked on the cap. Single pulse TMS was delivered using a single Magstim 200 via the coil of figure of eight. The coil position was maintained manually by the assistant and the handle of the coil point to posterior with an angle of 45 degree to the sagittal plane. Surface electromyography (EMG) electrodes are attached to the extensor carpi radialis (ECR) for EMG recording. The "hot spot" of the motor evoked potential (MEP) from ECR is first identified and marked for affected side. This spot will be used for all recordings on that side. The subject will

be considered MEP positive if more than or equal 50 μ V amplitude can be elicited in 50% of 10 successive trials while the muscle is at rest. If this criterion is not met with stimuli delivered at maximal intensity, the subject will be considered MEP negative.

Multimodal MRI imaging and Analysis

MRI data acquisition

Multimodal MRI data (T1, T2-flair, PCASL, DTI, MRS, resting-state fMRI and task-based fMRI) will be collected immediately pre-, post-, and 3months post treatment using a 3T Siemens MR system at the Clinical Imaging Research Centre using a 32 channel receive array head coil. Measurements will be made to assess changes in brain structure, metabolic status and connectivity as follows:

For anatomical delineation of the stroke lesion, and for normalization of functional data, a T1 weighted MPRAGE image (1mm³ isotropic voxels, 176 sagittal slices, TI/TE/TR=900/3/1950ms) and a T2 weighted FLAIR image (1x0.5x2mm, TI/TE/TR= 2500/78/2500ms) will be acquired.

To investigate changes in metabolic status of the tissue, a pseudo-continuous arterial spin labelled acquisition (PCASL) will be used to assess brain perfusion (3mm isotropic voxels). In addition, magnetic resonance spectroscopy will be used to measure concentrations of gamma-amino butyric acid (GABA, the main inhibitory neurotransmitter) and Glx (glutamate plus glutamine concentrations, the main excitatory neurotransmitter and its cycling intermediate) from a MEGA-PRESS localized volume in primary motor cortex (2x2x2cm volume)

For assessment of changes in neuronal connectivity, Diffusion Tensor Images (68 directions, b=1000, TE/TR=98/9100ms, plus 6 b=0 scans, 2mm isotropic voxels) will be collected to assess changes in fractional anisotropy related to structural connectivity. To investigate changes in functional connectivity, resting state connectivity data will be collected, as well as assessing changes in activation induced fMRI BOLD responses during an elbow extension task.

fMRI Activation paradigm

Subjects will be asked to extend their elbow to push against a bulb distally in a self-directed comfortable pace on a wooden/plastic board secured on their abdomen during fMRI investigation. All subjects will practice outside the scanner to reduce the mirror movements from the unaffected UL. For the task based acquisition, 12s of active task will be followed by 16s of resting (to allow the hemodynamic response to return to baseline). This will be repeated 9 times.

Neuroplasticity Investigation

fMRI imaging and image Analysis

Imaging is performed as above. Blood oxygenation level dependent (BOLD) images will be acquired to study the dynamic changes in brain activation in subjects during the investigation. The semi-automatic segmentation of the brain and atlas registration using FSL with the standard human brain atlas will be used to map the fMRI to atlas. Group analysis used in FSL will be applied to identify the functional activation and changes.

Multi-modality longitudinal brain function analysis

The modalities include T1, T2-flair, event-based fMRI BOLD, resting-state fMRI BOLD and DTI, as shown in Fig. 1. T1 image provides the anatomical structural information of the subject's brain. Haemorrhagic lesion also can be observed in T1 image. T2-flair provides the ischemic stroke lesion information. Event-based fMRI BOLD images will be used to find out the cortical activities that relate to subject's movement. The difference between pre- and pro- retaliation will be analysed to verify the retaliation performance. The difference between resting-state fMRI BOLD and event-based fMRI BOLD imaging is that the subject is requested to keep conscious but don't do any activity. It is used to recover functional connectivity inside subject's brain. In this study, the change of functional connectivity between pre- and pro- retaliation will be analysed as well. Diffusion-tensor magnetic resonance imaging, or DTI, is to map white matter tractography in subject's brain. The longitudinal changes of patients' white matter connectivity will be analysed during rehabilitation.

[figure not shown]

Figure 1. Multimodal MRI analysis diagram for early increased UL practice

The processing of the acquired multi-modality data is shown in Fig. 1. As the stroke may destroy part of patient's brain tissues, the stroke lesion(s) should be labelled using T2-flair image then convert to T1 image space. The brain structure should be accurately extracted from T1 structural image as it will be used as a middle point in fMRI-template, DTI-template co-registration and cortical thickness estimation as well. In the co-registration process, lesion areas should be excluded to prevent miss-alignment on the remaining healthy structures.

MRS data will be analysed using in-house based matlab scripts (GABA) and LCModel software (NAA, Cr, Cho, Glx). For LCModel an 18 metabolite basis dataset (TE appropriate) will be used. Concentrations will be corrected to absolute values using water referencing and, additionally, GABA concentrations will be provided relative to Cr. To account for tissue losses, concentrations will be corrected for tissue fraction based on the T1 weighted image (assuming concentrations are constant across tissue, no WM/GM differences). Concentrations of Lactate will not be tissue corrected as it exists in significant concentrations in CSF.

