The results of these studies showed that for stroke patients who had undergone a period of increased UL practice, there was a trend towards a decreased activation of contralateral motor area and supplementary motor areas and an increased activation in the ipsilesional motor area. This trend was approaching towards the activation pattern of normal healthy controls in their studies. However for stroke patients who had lower UL baseline motor capability, the gain in UL recovery after UL practice corresponded to an increase in both the ipsilesional and contralateral motor areas and supplementary motor areas. The neural reorganisation after increased UL practice after stroke varied across different individuals.

The complexity of neural reorganisation and the lack of studies on early increased UL practice on the neuroplasticity mechanism after stroke cause this important scientific area to be poorly understood. The understanding of this scientific gap is important because most rehabilitations occur early post-stroke and it is during this period that UL training can interact to support spontaneous recovery for optimal functional outcomes for patients.

Importance of Identification of Potential Imaging Biomarkers for Recovery

Another key to understanding the neurobiological mechanism of recovery is to identify potential biomarkers for recovery at early post-stroke and its interaction with UL practice. In a study by Marshall et al, it showed a correlation between the results of early task-related fMRI with the motor recovery. Marshall et al suggested that the recovery related activation pattern justified the investigation on early intervention to enhance the recovery process. In a study by Yin et al, it was reported that a biomarker can potentially be identified for UL recovery after stroke using volume-based measurement and diffusion tensor imaging (DTI) based FA (Fractional Anisotropy) analysis.

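### The imaging analyses are described as change over time in patients, which does not match the stated aim of finding what SURE does to neuroplasticity and how the two groups differ

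*Protocol*

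**What the plan says.** **Aim.** Protocol section 5.1 gives the purpose of the fMRI visits as "to determine if the increased UL activity in the" SURE program has a positive influence on the brain. Section 11.1 calls the trial a pilot and says results from each group will be examined in "detail to determine the difference in brain neuroplasticity between the control and experimental groups".

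**Analysis in section 6 (multi-modality longitudinal brain function analysis).**
- Task fMRI: "The difference between pre- and pro- retaliation will be analysed to verify the retaliation performance".
- Resting state: "the change of functional connectivity between pre- and pro- retaliation will be analysed as well".
- DTI: "The longitudinal changes of patients' white matter connectivity will be analysed during rehabilitation".

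None of these sentences names an arm. The imaging text just before them adds "Group analysis used in FSL will be applied to identify the functional activation and changes", without saying which groups or which contrast.

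**Analysis in section 11.2.** For task fMRI it says "Comparison of activation in primary motor cortex, secondary motor cortex and cerebellar hemisphere for bilateral sides will be done by comparing mean percentage signal change", together with voxel counts, geometric centres and a laterality index. For resting state and DTI it names the software and the normalisation method. Neither paragraph names an arm contrast. The same section does name the two arms when it describes the upper-limb outcomes and the accelerometer measures.

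**Setting.** Patients are admitted within 21 days of stroke (3.3), both groups continue routine therapy (5, 8.6), and section 1.1 takes spontaneous recovery in this phase as given: "it is during this period that UL training can interact to support spontaneous recovery for optimal functional outcomes for patients".

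**The concern.** A pre-to-post difference in patients estimates the sum of natural recovery, routine therapy and any program effect. Only a comparison with the randomised control arm removes the first two. The protocol plans scans in both arms at the same three time points, so the comparison is available, but the analysis text does not use it. Instead it attaches a conclusion, verification, to the one quantity that cannot separate these sources.

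At stake is the use of imaging to support the second hypothesis (that increased practice influences neuroplasticity positively) and the SURE-specific statements in 2.4a and 5.1. An analyst who followed section 6 literally could report a recovery pattern common to both arms, and a reader could take it as an effect of SURE. The point concerns task fMRI, resting state and DTI. The MRS analysis is left aside.

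**Working it through.** **1. Aim and analysis side by side.**

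| Place in protocol | Quantity | Arms compared? |
|---|---|---|
| 5.1, fMRI sentence | Effect of SURE's increased activity on the brain | Implied by the aim |
| 11.1 | Difference in neuroplasticity, control versus experimental | Yes |
| 6, task fMRI | Pre-to-post difference | No |
| 6, resting state | Pre-to-post change in connectivity | No |
| 6, DTI | Longitudinal change in patients | No |
| 6, FSL group analysis | Undefined; may mean multi-subject mapping | Not stated |
| 11.2, fMRI | Regions and sides of the brain, laterality index | No |
| 11.2, resting state/DTI | Software and normalisation | No |

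**2. Inputs for an illustration.** From the protocol: 10 per arm (3.1) and significance at 0.05 (11.2; two-sided is assumed because sidedness is not stated). The sample size rests on feasibility (11.1), so there is no planned effect size or power to reproduce. The protocol gives no figure for change in control patients. Assumed: no SURE effect, and the same standardised change d in both arms, in units of the SD of change. At a pre-post correlation of 0.5 this equals the baseline SD, since SD of change = SD × √(2(1 − 0.5)) = SD.

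**3. Pre-post test when SURE does nothing.** Power of a paired t-test: noncentral t with n − 1 degrees of freedom and noncentrality d√n. For d = 0.5 the noncentrality is 0.5 × √10 = 1.58 in one arm and 0.5 × √20 = 2.24 in all patients.

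| Shared change d | SURE arm, n = 10 | All patients, n = 20 |
|---|---|---|
| 0 | 5.0% | 5.0% |
| 0.3 | 13.6% | 24.7% |
| 0.5 | 29.3% | 56.5% |
| 0.8 | 61.6% | 92.4% |
| 1.0 | 80.3% | 98.9% |

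A separate simulation (20,000 trials per setting) gave 13.9%, 29.0% and 61.9% for the SURE arm and 24.7%, 56.0% and 92.7% for all patients at d = 0.3, 0.5 and 0.8. With a shared change of 0.5 baseline SD and correlation from 0.3 to 0.7, the ranges are 22–45% (SURE arm) and 44–78% (all patients).

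**4. Testing each arm separately does not repair this.** The chance of significance in SURE but not in control, with no program effect, is p(1 − p):
- d = 0.5: 0.293 × 0.707 = 21%
- d = 0.8: 0.616 × 0.384 = 24%
- d = 1.0: 0.803 × 0.197 = 16%

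**5. Between-arm test.** Under the same assumptions a t-test on change scores rejected in 4.9% to 5.2% of 40,000 simulated trials at shared changes of 0 to 1.0 SD. A baseline-adjusted comparison rejected in 5.0% to 5.2% at 0.3 to 0.8 SD.

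**6. What the between-arm test can detect.** Noncentral t with 18 degrees of freedom and noncentrality d√(10/2), where d is now the true difference in change between arms. Power is 18.5% at 0.5 SD, 39.5% at 0.8 SD and 56.2% at 1.0 SD; 80% needs about 1.3 SD.

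**The case against.** A reader might infer that the protocol credits shared recovery to SURE and leaves the control scans out as a comparator. The document does not say so. Section 11.1 makes the between-group difference the target, and section 2.2 speaks of biomarkers under both programs. Both arms are scanned at the same visits, and the imaging analysts are blinded to group (6.1, 8.5), a safeguard that serves a group comparison. The verification sentence does not mention SURE, and rehabilitation there may include the routine therapy that both arms receive. That reading is therefore not supported.

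It can also be said that section 6 describes what each modality provides and is not a statistical model, that within-subject change is the natural input to an arm comparison, and that contrasts are often left to an analysis plan, which is not at hand here. The illustrative rates rest on an assumed change and on t-tests that the protocol does not specify for these endpoints. The SURE-arm figure also presupposes knowledge of allocation, which the blinded analysts lack until unmasking.

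All of this limits the point without removing it. The protocol does more than leave a model open. It states change over time as the contrast, gives one such contrast the role of verification, and names arms for other outcomes in 11.2 but not for these. Section 6.1 places unmasking at the end of the fMRI analysis and mentions neither coded group labels nor a later comparison by arm.

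**Conclusion.** The point holds as a mismatch between aim and analysis. Sections 5.1 and 11.1 ask what SURE does and how the groups differ, while sections 6 and 11.2 describe only change over time, regions and sides of the brain for task fMRI, resting state and DTI. In patients recruited within 21 days of stroke, such change could be misread as a program effect. It does not follow that this trial will make that error, or that the control scans are excluded.

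The rates of about 14–62% in the SURE arm and 25–92% in all 20 patients, against about 5% between arms, illustrate the risk. They depend on a shared change of 0.3 to 0.8 SD, normal data, a two-sided 5% level and no SURE effect, and they do not predict the results. The change is worth making because it is cheap and lets the randomised design serve the stated imaging aim. The pilot status keeps the weight of the point moderate.

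**What to change.** In section 6 and in the fMRI and resting-state/DTI paragraphs of 11.2:

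- State that the inferential imaging analysis is SURE versus control for each measure already listed, at post-intervention and at 3 months, adjusted for the subject's own pre-intervention scan. For voxelwise work in FSL, specify a group-by-visit contrast on within-subject differences, and say what the group analysis compares.
- Report each result as an estimate with a 95% confidence interval.
- Label within-arm change as descriptive, and remove the wording that a pre-to-post difference verifies rehabilitation.
- In 6.1, either give the imaging analysts coded group labels (A and B) so that the contrast can be run before unmasking, or state that it is run after unmasking.

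The cost is wording and one contrast on scans already planned; no visit or patient is added. The downside is precision. With 10 per arm an unadjusted comparison of change has a 95% interval half-width of about 2.10 × √(2/10) = 0.94 SD of change, and about 40% power at 0.8 SD. Fewer imaging results will reach significance, and they should be presented as exploratory.
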